3.8.4. Physician Satisfaction Agreement Scale

After the completion of the procedure, the surgeon will be asked to rate the experience of using IC for each patient using the PSAS:

“Compared to the use of saline treatment, my ability to assess ureteral patency was improved after the addition of IC”

1 = Strongly Agree

2 = Agree

3 = Neither Agree nor Disagree

4 = Disagree

5 = Strongly disagree

The surgeon is considered satisfied with the IC treatment if his/her rating is either a 1 (Strongly Agree) or a 2 (Agree); otherwise, the surgeon is considered unsatisfied with the IC treatment.

Overall Satisfaction = Yes if PSAS is 1 or 2, otherwise

Overall Satisfaction = No

Physician who did not provide rating (missing data) will be grouped in the ‘No’ group for overall satisfaction analysis.

3.8.5. Concordance in Conspicuity Assessments between the Surgeons and the Blinded Central Readers

All randomized subjects will serve as his/her own control by receiving a dose of normal saline prior to receiving the randomized IC dose. The surgeon will be blinded to the IC dose a subject receives. In addition, each qualified subject must have 2 kidneys, resulting 4 observations of conspicuity score per subject from the surgery and four observations from the blinded central readers.

The following notation will be adapted for each conspicuity score for a given subject:

- CS_{SL} is the conspicuity score from the left ureter after saline injection
- CS_{SR} is the conspicuity score from the right ureter after saline injection
- CS_{IL} is the conspicuity score from the left ureter after IC injection
- CS_{IR} is the conspicuity score from the right ureter after IC injection

After the videography is read by the central blinded reader, each subject will then have 4 pairs of conspicuity scores. For example, CS_{SL} from the surgeon and the CS_{SL} from the central reader. Because the conspicuity has value of 1, 2, 3, 4, or 5, the difference in each pair of conspicuity scores between the surgeon and the blinded central readers will be derived and it will have a possible value ranging from (-4 to +4). Based on the difference in each pair of conspicuity score, a new dichotomized concordance response variable will be derived as

- Concordance Response = Yes if the difference in conspicuity score is within +/- 1 point. That is, the difference is ranged from (-1 to +1), inclusive.
- Concordance Response = No if the difference in conspicuity is more than 1 point

4. STUDY POPULATION SUMMARIES

All study population summaries will include 2 randomization groups plus an ‘Overall’ column to display the summary statistics across all subjects.

Study population data listing by individual subject will be prepared for all study population endpoints, including the observed value and derived variables.

4.1. Disposition

A summary table (**Table 14.1.1.1**) will provide frequency counts for subject disposition, including all enrolled subjects, randomized subjects, treated subjects (Saline or IC), subjects who completed study, subjects who did not complete study, and reason for not receiving Saline injection or IC injection, and reasons for study discontinuation.

Primary reason for early termination of study will include

- 1) Adverse Event
- 2) Study Non-compliance
- 3) Lost to Follow-Up
- 4) Physician Decision
- 5) Sponsor Decision
- 6) Subject Decision
- 7) Other

If a subject who receives a dose of normal saline injection and fails to receive a dose of IC, the subject will be considered to have discontinued study drug treatment. Reason for treatment discontinuation will be captured and tabulated. Moreover, the disposition table will identify number (%) subjects included for safety analysis set, efficacy analysis set (mITT), and efficacy per protocol (PP) analysis set.

Another summary table (**Table 14.1.1.2**) will be produced to provide number of subjects in the safety, mITT, and efficacy PP analysis set by investigator and will display the center with the highest enrollment first.

Disposition summary will be based on the ITT analysis set.

4.2. Demographics and Baseline Characteristics

The demographic summary (**Table 14.1.2.1**) will include descriptive statistics for age, age group (age <65, age >=65, >=75 years), sex, race, ethnicity, weight, height, and body mass index (BMI) at baseline for overall and by treatment group.

Baseline characteristics and patient population characteristics will also include the following study surgery information:

- 1) Surgery duration (hours), method of surgery (cystoscopic, robotic, open, laparoscopic, other), and surgeon's specialty
- 2) Requiring (yes/no) fluid to be instilled into the bladder
 - a. If Yes, the amount and type of fluids
- 3) Type, amount, and timing (relative to the start time of saline injection) of hydration
- 4) Use of any diuretics during the procedure (yes/no)

Demographics and baseline characteristics will be tabulated for the safety analysis set with no formal inferential tests. The same demographics table will also be prepared for the mITT analysis set (**Table 14.1.2.2**).

4.3. Medical History

All medical history data captured will be mapped using MedDRA (version 22). Subjects with medical history by SOC and preferred term will be tabulated by randomization group and study overall (**Table 14.1.3**) based on the safety analysis set.

4.4. Protocol Deviations

All protocol deviations will be identified and will be classified as either an 'Important Protocol Deviation' or 'Protocol Deviation'.

Important Protocol Deviation: An Important Protocol Deviation is a protocol deviation that may significantly impact the completeness, accuracy, and/or reliability of the study data or that may significantly affect a subject's rights, safety, or well-being. Examples may include:

- Failure to meet all entry criteria;
- Non-compliant with study drug treatment regimen;
- Did not receive randomized treatment due to dosing error;
- Use of prohibited concomitant medications;

Protocol Deviation: Any alteration/modification, divergence or departure from the IRB-approved protocol. A protocol deviation is an unanticipated or unintentional divergence or departure from the expected conduct of an approved study that is not consistent with the current research protocol, or consent document.

All protocol deviations will be tabulated by protocol type, protocol deviation category for each treatment group and study overall (**Table 14.1.4**) based on the safety analysis set.

4.5. Treatment Compliance

Doses of study medication (Saline and IC) will be administered to the study subjects under the observation of study personnel while confined to the study site. The exact time of administration of study medication will be documented within each subject's eCRF.

No formal Compliance data will be tabulated for the study report.

4.6. Prior and Concomitant Medications

All prior and concomitant medications will be mapped using WHO drug (version September 2019). Subjects with prior and concomitant medications will be tabulated by medication class and drug standardized name. The medication class will be the WHO Drug ATC level 3 text if available, otherwise, ATC level 2 text will be the medication class (**Table 14.1.5.1**). The prior and concomitant medications summary will be based on the safety analysis set.

All efforts will be made to ensure the capture of onset/stop dates of a medication. If at the end there are missing dates in the concomitant medication dataset, the following rules will be implemented for the purpose of analysis.

Concomitant meds will include medications with end-date that on or after the surgery date when present or if ongoing is checked. When ongoing is not checked and the end-date is partial the following rules will be used to determine if a medication is concomitant.

- a) EXCLUDE a medication if the year is before the surgery
- b) EXCLUDE a medication if the year is the same year but the month is before the surgery;
- c) INCLUDE a medication if the year is the same year as the surgery but the month is missing

When end-date is completely missing, the med will be accounted as concomitant medication.

Concomitant other procedures will be mapped using MedDRA version 22. All other procedures performed during the study will be tabulated by system organ class and preferred term (**Table 14.1.5.2**).

5. EFFICACY ANALYSIS

Efficacy data will be displayed by treatment group except PSAS and TTV.

All efficacy analyses will be based on the Efficacy analysis set (mITT Population). Although the PP analysis set is defined in [Section 3.3](#) efficacy analysis based on the PP analysis set will not be routinely provided. That is, when number of mITT subjects excluded from the efficacy PP analysis set is more than 10% of the mITT analysis set, then efficacy analysis will also be performed based on the efficacy PP analysis set to evaluate the consistency and the robustness of the efficacy conclusion drawn from the mITT analysis set.

Efficacy data listing by individual subject will be prepared for all efficacy endpoints, including the observed value and derived variables.

5.1. Conspicuity Score from the Central Readers

In this study each subject will serve as his/her own control and each subject will have repeated measures from the same treatment (1 from the left and 1 from the right ureter); therefore, each subject is expecting to contribute 4 observations for conspicuity endpoint. The recording videography will be read by the surgeon (who is unblinded for treatment and blinded for IC dose) and by two center readers who is blinded to the treatment (Saline vs IC) and IC dose. The score from the central readers will be the source for the primary endpoint analysis and the conspicuity score provided by the surgeons will be utilized for concordance analysis (see [Section 5.5](#) for details).

There will be 2 central reviewers to watch each video after the videos are blinded. The ratings are acceptable for consistency if the scores from the two independent reviewers for a ureter under the same treatment are within (+/-) 1 point. In this case, the average score across the two reviewers will be the final score from the central reader. Otherwise, a third independent reviewer (a judicator) will review the same video and this judicator's score will be the final score from the central reader.

As indicated earlier in [Section 3.7](#) the summary table for this endpoint will include 3 treatment groups, namely IC High Dose, IC Low Dose, and Saline Group. It is expected that the sample size (n) for the Saline group will be twice the size of the sample size for the IC High dose and IC Low Dose.

The treatment effect on the conspicuity score will be evaluated using a Generalized Estimating Equation (GEE) for Repeated Measures to control for the intra-subject correlation by fitting a proportional odds model to evaluate the treatment effect. A full model (**Model 1**) will provide the chi-square tests (Score Statistics for Type 3 GEE Analysis) for the effects from treatment (IC High dose / IC Low dose, Saline), ureter (left side ureter vs right side ureter), and treatment*ureter interaction on the response based on multi-normal distribution for an ordinal

response. The model estimates the cumulative logits of better outcome (conspicuity=5) to the poor outcome (conspicuity=1). Since it is expected that the interaction effect will not be statistically significant ($p > 0.10$), a reduced model (**Model 2**) will also be used in which the interaction effect will be dropped. The goodness of fit of the models (Full model vs the Reduced model) will be evaluated. A REPEATED statement will be used to control for the repeated measures within a subject. The difference between the IC high dose vs saline, the IC low dose vs saline will be presented in the summary along with the estimates and 95% confidence intervals of the estimates. Effect of a source (treatment, ureter, treatment*ureter interaction in full model) will be determined based on the Score Statistics for Type 3 GEE Analysis.

For the primary endpoint analysis, GEE models will be fitted separately for each comparison, namely IC High dose vs Saline, and IC Low dose vs Saline, and IC High dose vs IC Low dose.

An example of SAS syntax is showing below for this analysis, in which the conspicuity is treated as an ordinal response variable and a proportional odds model is used model the better response compared to the poorer response. Stokes et al. (2000)³ recommended that the null hypothesis of treatment effect would be based on the score statistics for Type 3 GEE analysis, whereas the parameter will be the GEE parameter estimates with the empirical standard error because the Z and the Wald statistic generally produce more liberal p-value than the score statistic.

In this example, the treatment is a binary code; IC High dose=1 and Saline=0. For analysis of IC Low dose vs Saline, IC Low dose=1 and Saline=0; when comparing IC High dose vs IC Low dose, IC High dose=1 and IC Low dose=0.

```

PROC GENMOD DATA=respH descending;
  CLASS USUBJID URETER(ref='Right') TRT (ref='Saline');
  MODEL conspicuity = trt ureter trt*ureter
    /LINK=clogit DIST=mult TYPE3; (Model 1)
  REPEATED subject = Usbjid / type=ind;
  ESTIMATE 'OR: IC vs Saline' trt 1 -1/ exp;
  ods output Estimates=OR1 GEEEmpPEst=est1 Type3=pval1;
  Run;

PROC GENMOD DATA=respH descending;
  CLASS USUBJID URETER(ref='Right') TRT (ref='Saline');
  MODEL conspicuity = trt ureter
    /Link=clogit DIST=mult TYPE3; (Model 2)
  REPEATED SUBJECT = Usbjid / type=ind;
  ESTIMATE 'OR: IC vs Saline' trt 1 -1/ exp;
  ods output Estimates=OR2 GEEEmpPEst=est2 Type3=pval2;
  Run;

```

Where:

³ Stokes ME, David CS, Koch GG (2000). Categorical Data Analysis using the SAS System 2nd Edition (page 485).

1. Dataset respH include subjects from IC High dose only.
2. The ‘descending’ option indicates that the ordered values are listed in descending order.
3. Conspicuity score (1, 2, 3, 4, or 5)
4. ‘TRT’ is Treatment (coded to IC or Saline)
5. ‘URETER’ is coded to ‘Left’ or ‘Right’
6. ‘USUBJID’ is the unique Subject Identification
7. REPEATED statement controls the intra-subject correlation due to repeated measures. In this example, independent correlation matrix is used.
8. Three output datasets:
 - a. OR=estimated odds ratio (IC /Saline)
 - b. EST= Analysis of GEE Parameter Estimates based on Empirical Standard Error Estimates
 - c. PVAL= P-value for each effect in the model per Score Statistics For Type 3 GEE Analysis

The analysis summary table (**Table 14.2.1.1**) will include distribution of conspicuity score in each treatment group by ureter (left vs right and overall), p-value based on score statistics for Type 3 GEE analysis, odds ratio estimates and standard error, and 95% confidence intervals for the odds ratio. Three treatment group comparisons will be provided, namely difference between IC High dose vs Saline, IC Low dose vs Saline and IC High dose vs IC Low dose (an exploratory analysis).

The summary table will display the nominal p-values from each comparison (High dose vs Saline, Low dose vs Saline, and High dose vs Low dose). However, the statistical significance of the normal nominal p-value between the IC High dose vs Saline and between the IC Low dose vs Saline will follow the rule defined in [Section 3.4](#) in order to control for family-wide type I error for the primary endpoint.

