2. OVERVIEW OF STUDY OBJECTIVES AND ASSESSMENTS

The primary objective of this study is to determine whether the use of Indigo Carmine 0.8% Injection, USP solution for injection (IC) provides a visualization advantage compared to saline when used as an aid in the determination of ureteral patency. Visualization will be measured by a 5-point conspicuity score as follows:

- 1 = No jet observed
- 2 = Weak jet, little color contrast
- 3 = Color contrast or significant jet flow
- 4 = Strong jet flow with good color contrast
- 5 = Strong jet flow with striking contrast in color

Secondary objectives are to assess:

1. To evaluate the safety profile of IC when used as an aid in the determination of ureteral patency.
2. To determine physicians' overall satisfaction with the IC treatment by assessing the proportion of surgeons who agree using the 5-point Physician Satisfaction Agreement Scale (PSAS) with the statement:

“Compared to the saline treatment, my ability to assess ureter patency was improved after the addition of IC.”

- 1. Strongly Agree
- 2. Agree
- 3. Neither Agree nor Disagree
- 4. Disagree
- 5. Strongly Disagree

A surgeon's evaluation is considered satisfactory if the rating is either a 1 (strongly agree) or 2 (agree).

3. To determine proportion of responders. To determine proportion of subjects meeting the responder definition in conspicuity score following IC treatment based on the blinded central reviewer's assessment. A subject is a responder when there is ≥ 1 point difference in the conspicuity score following the IC vs saline treatment (IC – Saline ≥ 1) and the conspicuity score following the IC treatment is (3, 4, or 5). The responder criteria will be assessed separately for each ureter for each subject.

4. To describe the time to visualization (TTV) of blue color in the ureteral jets flow following IC treatment when used as a visualization aid during urological and gynecological surgical procedures
5. To determine the IC pharmacokinetic profile in a subset of subjects from 2 investigational sites.
6. An exploratory comparison will be done on the difference between the IC high dose vs IC low dose. Surgeons will be blinded to the dose of IC.

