The study will enroll approximately 116 subjects from approximately 10 – 20 study centers in the United States. Subjects scheduled for urological or gynecological surgical procedures, age 18 to 85 years inclusive, will be screened for participation. Screening will occur within 30 days before study drug administration (Day of Surgery). After signing the informed consent, medical history, physical examination, baseline laboratory testing, pregnancy testing, 12-lead ECG, and vital sign measurements will be completed during the screening visit. Any procedure done for the purpose of the surgery before the date of signing the informed consent may be used as long as it was within 30 days of the scheduled surgery date.

On the day of surgery (Day 1) the subject will be evaluated for eligibility for randomization. Eligible subjects will be randomized to receive a dose of either IC high dose (5 mL) or IC low dose (2.5 mL). Each randomized subject will serve as his/her own control by receiving a dose of normal saline prior to receiving the randomized IC dose. The surgeon will be blinded to the IC dose a subject receives. Time of injection of saline and IC will be captured.

To evaluate the efficacy outcomes, each subject will first be injected intravenously with 5 mL 0.9% saline. The ureteral orifices/flow will be observed and video recorded for 10 mins. The time period that will be captured on video is from injection to 10 minutes post injection. If both ureters cannot be visualized simultaneously, then alternating 15-30 second images of each ureter or ureteral orifice will be obtained. The process will be repeated in the same patient for the IC dose. Hence, each subject will have 2 videos and each will be about 10 minutes in length.

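### The exploratory High-versus-Low conspicuity model leaves out each subject's saline score and may give up power on the only randomized comparison (minor)

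*SAP*

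**What the plan says.** SAP Section 2 assigns the IC dose at random, high (5 mL) or low (2.5 mL). Saline is not randomized: "Each randomized subject will serve as his/her own control by receiving a dose of normal saline prior to receiving the randomized IC dose". The dose contrast is among the listed objectives: "An exploratory comparison will be done on the difference between the IC high dose vs IC low dose".

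Section 5.1 fits a separate GEE proportional-odds model for each of three comparisons: High versus Saline, Low versus Saline, and High versus Low. Model 1 is "MODEL conspicuity = trt ureter trt*ureter", and Model 2 drops the interaction. For the dose contrast the coding is "when comparing IC High dose vs IC Low dose, IC High dose=1 and IC Low dose=0". Saline has no level under that coding, and neither model has a saline-score term. Table 14.2.1.1 reports the odds ratio, its standard error, the 95% interval and a nominal p-value, and the SAP labels this row "IC High dose vs IC Low dose (an exploratory analysis". Section 3.4 confines type I error control to the two IC-versus-saline hypotheses.

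Three other places touch the issue:

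- Section 5.3 compares doses on a responder proportion built from the IC-minus-saline difference.
- Section 5.6 allows covariates to be added to the Section 5.1 models if the data warrant it. Its open-ended list names surgery type, surgeon specialty and demographics, but not the saline score.
- Section 3.7 allows the saline group to be split by IC dose in data presentations.

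**The concern.** The two IC-versus-saline models compare treatments within a subject. High versus Low compares different subjects, so patient-to-patient differences in jet strength, hydration, optics and surgery type all enter as noise. A measurement that may carry part of that variation is already planned: the saline score. It is taken before IC, so dose cannot affect it. It is read by central readers blinded to treatment and dose, on the same scale and the same ureters. The efficacy set in Section 3.3 requires a video after each injection, so the score should exist for almost every subject.

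At stake is the efficiency of the one contrast that randomization supports directly, in a trial with fewer than 50 efficacy subjects per dose. Section 5.6 does not settle this, because a covariate chosen only if data warrant it is not pre-specified.

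**Working it through.** **Inputs from the SAP**

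- Total enrollment is about 116 (Section 2). The 21 subjects treated before the conspicuity scale was developed are excluded from efficacy (Sections 3.2 and 3.3).
- Allocation is about equal, because Section 3.7 expects the saline group to be twice the size of each dose group.
- Dose is taken as the randomized factor, as Sections 2 and 3.7 say. One remark in Section 3.2 describes randomization as concerning IC versus saline. It does not fit those sections and should be reconciled with them.

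**The plan's own figures.** 116 − 21 = 95, and 95 × 0.5 = 47.5, which agrees with the SAP's 95 and 47–48. The 116 cannot be reproduced because its assumptions are redacted. No power is stated for High versus Low.

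**Assumed.** The correlation r between a subject's saline and IC scores is not in the documents. Every result below is conditional on it.

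**Step 1: approximation on the mean-score scale.** Adjusting for a baseline multiplies the variance of the dose difference by 1 − r². With n = 47.5 per dose and two-sided α = 0.05, power ≈ Φ(d√(n/2)/√(1 − r²) − 1.96). At an assumed d = 0.5:

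- r = 0: 0.5 × √23.75 = 2.437, and Φ(2.437 − 1.96) = 68%.
- r = 0.5: 2.437/0.866 = 2.814, and Φ(2.814 − 1.96) = 80%.

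| r | Variance reduction | Equivalent subjects, 95/(1 − r²) | Power at d = 0.5 |
|---|---|---|---|
| 0 | 0% | 95 | 68% |
| 0.1 | 1% | 96 | 69% |
| 0.3 | 9% | 104 | 72% |
| 0.5 | 25% | 127 | 80% |
| 0.7 | 49% | 186 | 93% |

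The difference detectable with 80% power is (1.96 + 0.84) × √(2/47.5) = 0.57 SD unadjusted. It becomes 0.55, 0.50 and 0.41 at r = 0.3, 0.5 and 0.7.

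**Step 2: the planned type of model.** The simulation used a proportional-odds GEE with independence working correlation and robust standard errors, 95 subjects with two ureters each, an assumed latent dose shift of 0.5 SD, and 400 trials per setting. The covariate was the subject's mean saline score.

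| Observed r | Log-OR without → with | SE without → with | Power without → with |
|---|---|---|---|
| 0 | 0.885 → 0.888 | 0.342 → 0.344 | 73% → 73% |
| 0.19 | 0.860 → 0.876 | 0.342 → 0.345 | 70% → 71% |
| 0.37 | 0.864 → 0.960 | 0.342 → 0.345 | 68% → 78% |
| 0.56 | 0.838 → 1.062 | 0.343 → 0.345 | 69% → 89% |

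The Monte Carlo error of each power is about √(0.7 × 0.3/400) = 2.3 percentage points. As a check on the last row, 0.838/0.343 = 2.44 gives Φ(0.48) = 68%, and 1.062/0.345 = 3.08 gives Φ(1.12) = 87%. Both are close to the simulated values.

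The log-OR standard error barely moves. The power comes from a larger, conditional log-odds ratio. On the mean-score scale under the same data model, the variance does fall: the ratios were 0.97, 0.86 and 0.67 at the three non-zero correlations. At r = 0 the ratio was 1.011, so the standard error grows by a factor of √1.011, about 0.5%.

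**The case against.** The strongest reply is that nothing is broken. Dose is randomized, so the unadjusted comparison is valid. The contrast is exploratory, its p-value is nominal, and the primary objective is IC versus saline. All of that stands, and it sets the priority.

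A reader might infer that chance imbalance in saline scores biases the dose estimate. It does not: such imbalance is sampling variation and is already reflected in the standard error. A reader might also infer that omitting the covariate widens the reported interval. On the odds-ratio scale of Table 14.2.1.1 the simulation does not show that, since the log-OR standard error was 0.342–0.343 without the covariate and 0.344–0.345 with it.

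The gain may also be small. The upper scores require good or striking color contrast, which undyed jets would rarely earn, so saline scores may sit near the floor and IC scores near the ceiling. Linear-model simulations at an assumed latent correlation of 0.6 show the sensitivity. One set of score assumptions gave a variance ratio of 0.59. Saline scores confined to 1–3 (50/35/15%), with 80% of low-dose IC scores at 4–5, gave 0.80 and moved power from 50 to 59%. Stronger floor and ceiling effects gave 0.89. The true score distribution is redacted, so a large loss cannot be claimed.

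Adjustment also has a cost in interpretation. A conditional odds ratio is not on the same scale as the two unadjusted IC-versus-saline odds ratios in the table. And borrowing the other ureter's score when one is missing would be a form of imputation, which Section 5.1.1 rules out for this table. Both points stand, and the fix allows for them.

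The partial cover elsewhere does not close the gap. The Section 5.3 responder is dichotomized, Section 5.6 is optional, and splitting saline summaries by dose shows imbalance without adjusting for it.

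**Conclusion.** The point holds as a minor efficiency improvement. The High-versus-Low model is between-subject and leaves out a pre-dose, blinded, same-scale measurement that the trial collects anyway. Depending on the unknown correlation, the cost in power ranges from nothing (r = 0) through about 10 points (r about 0.4) to about 20 points (r about 0.6). It is negligible below r of about 0.2. These figures rest on assumed correlations, score distributions and dose effects, and floor or ceiling effects could make them smaller.

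A reader might go further and conclude that the dose comparison is invalid or that the primary result is weakened. The documents support neither. Randomization protects the unadjusted contrast, and the IC-versus-saline models and their Hochberg control do not depend on it.

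**What to change.** In SAP Section 5.1, for High-versus-Low Models 1 and 2 only, pre-specify the subject's central-reader saline score as a single linear covariate. It can be the same-ureter score or the mean of the subject's available saline scores; the SAP should name one before the dose code is released. The mean is the form simulated above, and it needs no separate rule when one ureter is unscored. A linear term also accommodates half-point averages from the two readers.

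Label the adjusted result a conditional odds ratio. Print the planned unadjusted odds ratio beside it in Table 14.2.1.1, so that a figure comparable with the IC-versus-saline odds ratios remains. Because Sections 5.1.1 and 5.5.1 reuse the Section 5.1 model, add a line saying whether the covariate carries over to the sensitivity and surgeon-score tables.

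The cost is one model term, one extra table row and a sentence or two of text. It needs no new data and no change to alpha, and it does not touch the primary tests. If the scores turn out uncorrelated, the price is about 0.5% on the standard error on the mean-score scale.
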